9.4. Data source

The source document used will be electronic or physical medical record of the patient.

9.5. Study size

The population of this study consists of the ATTRv and ATTRwt patients included in studies B3461028 and B3461045 in Spain, who present with multisystem involvement (cardiac and neurological), who are currently receiving or have received treatment with tafamidis free acid 61 mg for at least 12 months; and who have a neurological follow-up of at least 12 months. To our knowledge, ~~co~~ ATTRv patients have been included in studies B3461028 and B3461045 studies in

Spain. Patients who respond to the inclusion criteria are estimated to be ~~cc1~~ with ATTRv and ~~cc1~~ with ATTRwt.

9.6. Data management

The investigator will collect data from patients included in an electronic Case Report Form specially designed for this study.

The number of patients will be a correlative number without any identifying value.

The information will be stored in a database which will in turn be associated with a file, detailing the permissions within the database.

9.6.1. Case report forms (CRFs)/Data collection tools (DCTs)/Electronic data record

As used in this protocol, the term CRF should be understood to refer to either a paper form or an electronic data record or both, depending on the data collection method used in this study.

A CRF is required and should be completed for each included patient. The completed original CRFs are the sole property of Pfizer and should not be made available in any form to third parties, except for authorized representatives of Pfizer or appropriate regulatory authorities, without written permission from Pfizer. The investigator shall ensure that the CRFs are securely stored at the study site in encrypted electronic form and will be password protected to prevent access by unauthorized third parties.

The investigator has ultimate responsibility for the collection and reporting of all clinical, safety, and laboratory data entered on the CRFs and any other data collection forms (source documents) and ensuring that they are accurate, authentic/original, attributable, complete, consistent, legible, timely (contemporaneous), enduring, and available when required. The CRFs must be signed by the investigator or by an authorized staff member to attest that the data contained on the CRFs are true. Any corrections to entries made in the CRFs or source documents must be dated, initialed, and explained (if necessary) and should not obscure the original entry.

The source documents are the hospital or the physician's chart. In these cases, data collected on the CRFs must match those charts.

9.6.2. Record retention

PFIZER CONFIDENTIAL

To enable evaluations and/or inspections/audits from regulatory authorities or Pfizer, the investigator agrees to keep records, including the identity of all participating patients (sufficient information to link records, e.g., CRFs and hospital records), copies of all CRFs, safety reporting forms, source documents, detailed records of treatment disposition, and adequate documentation of relevant correspondence (e.g., letters, meeting minutes, and telephone call reports). The records should be retained by the investigator according to local regulations or as specified in the clinical study agreement (CSA), whichever is longer. The investigator must ensure that the records continue to be stored securely for so long as they are retained.

If the investigator becomes unable for any reason to continue to retain study records for the required period (e.g., retirement, relocation), Pfizer should be prospectively notified. The study records must be transferred to a designee acceptable to Pfizer, such as another investigator, another institution, or to an independent third party arranged by Pfizer.

CC1

The investigator must obtain Pfizer's written permission before disposing of any records, even if retention requirements have been met.

9.7. Data analysis

Detailed methodology for summary and statistical analyses of data collected in this study will be documented in a Statistical Analysis Plan (SAP), which will be dated, filed and maintained by the sponsor. The SAP may modify the plans outlined in the protocol; any major modifications of primary endpoint definitions or their analyses would be reflected in a protocol amendment.

9.8. Quality control

The study will be governed by the basic ethical principles contained in the Declaration of Helsinki.

The highest levels of professional conduct and confidentiality will always be maintained and applicable national data protection laws will be followed at all times. The right to patient confidentiality is critical. The patient's identity in the study documents will be encrypted and only authorized persons will have access to personal details that could identify the patient if data verification procedures require it. The personal details that could identify the patient will always be confidential.

The investigator will collect data from patients included in a Case Report Form (CRF) specially designed for this study. The patient number to be provided will be a correlative number without any identifying value. The recruited patients will be entered via dedicated data entry software and stored in the study database. A Data Management Plan (DMP) will be developed in which we will

PFIZER CONFIDENTIAL

detail the different steps to be followed to ensure consistency of the data and to ensure data quality standards.

Random monitoring will be performed in at least 20% of sites included in the study. The study monitor will review the information recorded in the CRFs against the investigator in order to verify the data collected for all study variables.

Each participating investigator will be contacted by the study monitor whenever necessary in order to assist in the data collection process and to resolve any potential occurrences. Upon completion of the CRFs, the study monitor will review the CRFs and may ask the physicians questions (called queries) regarding the most important missing variables (according to a predefined list of key variables). In this phase, the queries will be generated electronically by 100% of the patients and the researchers must resolve them before the closure of the database. The investigator may contact the study monitor when necessary.

A personal statistical team of the CRO hired by the sponsor of the study, will be responsible for the treatment and analysis of the data collected in the CRF for subsequent statistical analysis.

9.9. Limitations of the research methods

The main limitation of the study is the small sample size. Another limitation may be related to the scarcity of the data collected during the follow-up visits, which may provide a partial view of the progression of the disease at the systemic level.

Other causes of neuropathy are also common, particularly for ATTRwt, which can reduce sample size.

9.10. Other aspects

N/A

10. PROTECTION OF HUMAN SUBJECTS

10.1. Patient information

All parties will comply with all applicable laws, including laws regarding the implementation of organizational and technical measures to ensure protection of patient personal data. Such measures will include omitting patient names or other directly identifiable data in any reports, publications, or other disclosures, except where required by applicable laws.

The personal data will be stored at the study site in *encrypted electronic and* form and will be *password protected* to ensure that only authorized study staff have access. The study site will implement appropriate technical and organizational measures to ensure that the personal data can be recovered in the event of disaster. In the event of a potential personal data breach, the study

PFIZER CONFIDENTIAL

site shall be responsible for determining whether a personal data breach has in fact occurred and, if so, providing breach notifications as required by law.

To protect the rights and freedoms of natural persons with regard to the processing of personal data, when study data are compiled for transfer to Pfizer and other authorized parties, patient names will be removed and will be replaced by a single, specific, numerical code, based on a numbering system defined by Pfizer. *All other identifiable data transferred to Pfizer or other authorized parties will be identified by this single, patient-specific code.* The investigator site will maintain a confidential list of patients who participated in the study, linking each patient's numerical code to his or her actual identity. In case of data transfer, Pfizer will maintain high standards of confidentiality and protection of patients' personal data consistent with the clinical study agreement and applicable privacy laws.

10.2. Patient consent

As this study does not involve data subject to privacy laws according to applicable legal requirements, obtaining informed consent from patients by Pfizer is not required

10.3. Institutional Review Board (IRB) or Independent Ethics Committee (IEC)

There must be prospective approval of the study protocol, protocol amendments, and other relevant documents (e.g., informed consent forms, if applicable) from the relevant IRBs/IECs. All correspondence with the IRB/IEC must be retained by the investigator. Copies of IRB/IEC approvals must be forwarded to Pfizer

10.4. Ethical conduct of the study

The study will be conducted in accordance with legal and regulatory requirements, as well with scientific purpose, value and rigor, and follow generally accepted research practices generally and described in:

PFIZER CONFIDENTIAL

11. MANAGEMENT AND REPORTING OF ADVERSE EVENTS/ADVERSE REACTIONS

This study protocol requires human review of patient-level unstructured data; unstructured data refer to verbatim medical data, including text-based descriptions and visual depictions of medical information, such as medical records, images of physician notes, neurological scans, X-rays, or narrative fields in a database. The reviewer is obligated to report adverse events (AEs) with explicit attribution to any Pfizer drug that appear in the reviewed information (defined per the patient population and study period specified in the protocol). Explicit attribution is not inferred by a temporal relationship between drug administration and an AE, but must be based on a definite statement of causality by a healthcare provider linking drug administration to the AE.

The requirements for reporting safety events on the non-interventional study (NIS) adverse event monitoring (AEM) Report Form to Pfizer Safety are as follows:

PFIZER CONFIDENTIAL

- All serious and non-serious AEs with explicit attribution to **any Pfizer drug** that appear in the reviewed information must be recorded on the case report Form and reported, within 24 hours of awareness, to Pfizer Safety using the NIS AEM Report Form.
- Scenarios involving drug exposure, including exposure during pregnancy, exposure during breast feeding, medication error, overdose, misuse, extravasation, lack of efficacy, and occupational exposure associated with the use of a Pfizer product must be reported, within 24 hours of awareness, to Pfizer Safety using the NIS AEM Report Form.

For these AEs with an explicit attribution or scenarios involving exposure to a Pfizer product, the safety information identified in the unstructured data reviewed is captured in the Event Narrative section of the report form, and constitutes all clinical information known regarding these AEs. No follow-up on related AEs will be conducted.

All the demographic fields on the NIS AEM Report Form may not necessarily be completed, as the form designates, since not all elements will be available due to privacy concerns with the use of secondary data sources. While not all demographic fields will be completed, at the very least, at least one patient identifier (e.g., gender, age as captured in the narrative field of the form) will be reported on the NIS AEM Report Form, thus allowing the report to be considered a valid one in accordance with pharmacovigilance legislation. All identifiers will be limited to generalities, such as the statement “A 35-year-old female...” or “An elderly male...” Other identifiers will have been removed.

Additionally, the onset/start dates and stop dates for “Illness”, “Study Drug”, and “Drug Name” may be documented in month/year (mmm/yyyy) format rather than identifying the actual date of occurrence within the month /year of occurrence in the day/month/year (DD/MMM/YYYY) format.

All research staff members must complete the following Pfizer training requirements:

- “*Your Reporting Responsibilities (YRR) Training for Vendors*”.

These trainings must be completed by research staff members prior to the start of data collection. All trainings include a “Confirmation of Training Certificate” (for signature by the trainee) as a

PFIZER CONFIDENTIAL

record of completion of the training, which must be kept in a retrievable format. Copies of all signed training certificates must be provided to Pfizer.

Re-training must be completed on an annual basis using the most current Your Reporting Responsibilities training materials.

[figure not shown]
12. PLANS FOR DISSEMINATING AND COMMUNICATING STUDY RESULTS

In the event of any prohibition or restriction imposed (e.g., clinical hold) by an applicable competent authority in any area of the world, or if the investigator is aware of any new information which might influence the evaluation of the benefits and risks of a Pfizer product, Pfizer should be informed immediately.

14. LIST

Not applicable

15. LIST OF FIGURES

Not applicable

ANNEX 1: LIST OF STAND ALONE DOCUMENTS

List of Principal Investigators.

PFIZER CONFIDENTIAL

Tafamidis

TRAMA B3461104 NON-INTERVENTIONAL STUDY PROTOCOL

Version 1.0, 17 February 2022

PFIZER CONFIDENTIAL

1 INTRODUCTION

This document contains the Statistical Analysis Plan (SAP) for the TRAMA study.

Transthyretin amyloidosis (ATTR) is a rare, progressive, clinically heterogeneous, and life-threatening disease caused by pathogenic mutations in the transthyretin (*TTR*) gene, resulting in the hereditary form (ATTRv), or due to factors related to aging, resulting in the natural or wild-type form (ATTRwt) of the disease.

ATTR is a systemic disease in which deposition of TTR amyloid insoluble fibers can occur in multiple tissues, including the peripheral nervous system, heart, kidneys, gastrointestinal tract, and eyes, resulting in, as most common phenotypes, peripheral and/or autonomic polyneuropathy (ATTR-PN), restrictive cardiomyopathy (ATTR-CM), or a mixed phenotype. More than 140 mutations in the *TTR* gene have been described, with different phenotypes based on the mutation that the patient has. However, with disease progression, unique phenotypes generally become mixed phenotypes where cardiomyopathy can be accompanied by polyneuropathy and vice versa. In the case of ATTRwt, although the disease usually manifests with cardiac symptoms, patients may present with sensorimotor and autonomic neurological disturbances, which in any case are less prominent in the clinical condition.

Cardiac transthyretin amyloidosis (ATTR-CM) is caused by extracellular deposition of TTR amyloid fibers at the cardiac level, both in the ATTRwt form and in the ATTRv form, resulting in restrictive cardiomyopathy that clinically manifests as heart failure (HF). At least 22 mutations associated with ATTR-CM have been described, with Val122Ile, Thr60Ala, Leu111Met and Ile68Leu being the most common mutations.

There is currently no published data on the use of Tafamidis free acid 61 mg in patients with ATTR-PN; therefore this study addresses an unmet medical need and may yield on the efficacy or Tafamidis non-free acid 61 mg in patients with mixed phenotype ATTRv and in ATTRwt patients with neurologic involvement.

2 PROTOCOL VERSION AND CRF

Protocol Version: v1.0 CCI

CRF Version: v1.0 CCI

2.1 Amendments to previous versions

Date	Sections that are modified in the PAE	Summary of changes	Reason for change
version 2.0 CCI	12.1 Primary objective	Inclusion of the definition of responder according to the scale change at 12 months compared to the initial data <4p in NIS, patients who have obtained less than 4 points in the NIS in month 12	It is included in the PAE to define the primary objective in the PAE and to be able to reflect the data in this regard in the statistical report.
version 2.0 CCI	12.2.1 Secondary objective 1	Add to the secondary objectives analysis of responders according to NIS at different months and according to the NIS-LL scale at different months, separately	It is included in the PAE to define the secondary objectives in the PAE and to be able to reflect the data in this regard in the statistical report.

3 OBJECTIVES AND DESIGN

3.1 Analysis Plan Objectives

The analysis plan proposed below details the aspects that should be known about the study and the statistical analysis methods to be used in order to apply them to the data collected and to meet the objectives of the study.

3.2 Primary and Secondary Objectives

Based on the outcomes from previous studies, the **hypothesis** of the present study is that Tafamidis free acid 61 mg decreases the progression of polyneuropathy caused by transthyretin amyloidosis in ATTRv and ATTRwt patients with neurological or mixed phenotype.

3.2.1 Primary objective

The study's primary objective is:

- To determine the efficacy of Tafamidis free acid 61 mg in ATTRv patients with neurologic involvement included in studies B3461028 and/or LTE (B3461045) in Spain through changes in the NIS scale at 12 months (See B3461104_Archive Note).

3.2.2 Secondary objectives

The secondary objectives of this study are:

- To determine the efficacy of Tafamidis 61 mg in ATTRv patients with neurologic involvement included in studies B3461028 and/or LTE (B3461045) in Spain using additional non-cardiac variables at 6, 12, 18, 24 and 36 months after the start of treatment.
- To determine the efficacy of Tafamidis free acid 61 mg in ATTRwt patients with neurological symptoms included in studies B3461028 and/or LTE (B3461045) in Spain, through non-cardiac variables at 6, 12, 18, 24 and 36 months after treatment initiation.
- To describe the extra-cardiac characteristics of ATTRv and ATTRwt patients included in studies B3461028 and/or LTE (B3461045) in Spain with mixed phenotype treated with Tafamidis free acid 61 mg.

3.3 Study design

Retrospective, multicenter, non-interventional, observational and descriptive study. It will by no means interfere with the investigator's decision on the most appropriate medical care or treatment for the patient or carrier.

4 STUDY POPULATION

The current study population consists of ATTRv and ATTRwt patients who have participated in studies B3461028 and B3461045 in Spain, with cardiac and neurologic involvement receiving or who have received Tafamidis free acid 61 mg for at least 12 months, and who are in neurological follow-up for no less than 12 months. According to the protocol, patients who meet the inclusion criteria are estimated to be: 10 with ATTRv and 10 with ATTRwt.

Individuals participating in the TRAMA study must meet all of the inclusion and none of the exclusion criteria.

4.1 Inclusion Criteria

Patients must meet all of the following inclusion criteria to be eligible for this study:

1. Be of legal age (>18 years).
2. Have participated in studies B3461028 and/or B3461045 in Spain.
3. Have been treated for at least 12 months with Tafamidis free acid 61 mg.
4. Have a minimum of 12 months of neurological follow-up after starting treatment with Tafamidis free acid 61 mg and have data from previous neurological evaluation or at the time of starting treatment with Tafamidis free acid 61 mg.
5. Have been diagnosed with ATTR amyloidosis polyneuropathy (ATTR-PN), based on any of the following criteria:
 - a. Decreased amplitude in EMG studies, at least two nerves below normal, excluding median, or other nerve entrapment sites.
 - b. A reduction in amplitude by more than 50% by at least two nerves above the patient's baseline value, excluding the median.
 - c. Two different altered fine fiber tests (Sudoscan, CRS, RR interval variability, skin biopsy, etc.).
 - d. A clinical picture consistent with small fiber neuropathy (painful or dysautonomic) and an altered fine fiber test.

4.2 Exclusion criteria

Patients who meet any of the following criteria will not be included in the study:

1. Treatment with Tafamidis free acid 61 mg for less than 12 months.
2. Not having a minimum of 12 months of neurological follow-up after starting treatment with Tafamidis free acid 61 mg.
3. Etiological diagnosis of polyneuropathy other than ATTR.

5 POPULATION TO BE ANALYZED

The patient's classification is defined below based on compliance with the screening criteria:

- ***Evaluable patients*** are defined as those who meet all of the inclusion criteria and none of the exclusion criteria described in the protocol.
- ***Non-evaluable patients*** are defined as those who fail to meet any of the inclusion criteria or meet one or more exclusion criteria.

Information regarding the screening criteria in the form of a binary variable (Yes / No) is recorded on the CRF for each item described.

Several of these criteria can be checked against the data collected in the CRF. The criteria that will be verified in order to define the evaluable population are described below:

Inclusion Criteria

Patients must meet all of the following inclusion criteria to be eligible for this study:

1. *Be of legal age (>18 years).*

Age of all patients at enrollment will be checked to ensure they are 18 years old or above.

2. *Have participated in studies B3461028 and/or B3461045 in Spain.*

A check will be carried out to ensure patients have answered 'yes' to one of the following questions:

- Has the patient participated in study B3461028?
- Has the patient participated in study B3461045?

It will also be confirmed that they have collected the date of the consent indicated for the corresponding previous study.

3. Have been treated for at least 12 months with Tafamidis free acid 61 mg.

The difference between the Tafamidis 61 mg end date minus its start date will be checked to ensure it is at least 12 months, or otherwise the Tafamidis 80 mg end date minus its start date is at least 12 months:

(End date* - start date* \geq 12 months)

*Dates for Tafamidis 61 mg or 80 mg

In such cases where they are on treatment with Tafamidis 61 mg, the date of inclusion in this study will be considered as “End Date”.

4. Have a minimum of 12 months of neurological follow-up after starting treatment with Tafamidis free acid 61 mg and have data from previous neurological evaluation or at the time of starting treatment with Tafamidis free acid 61 mg.

For all patients, the difference between the last follow-up and the start of treatment with Tafamidis (61 or 80 mg) will be checked to ensure it is at least 12 months.

(Last follow-up date - treatment start date* \geq 12 months)

*The first date of treatment with Tafamidis 61 mg or 80 mg

A check will be carried out to ensure that data is available for all patients in the following neurological variables, in the 12 months prior to inclusion in the studies (B3461028 and/or LTE B3461045) or at inclusion in the same studies (start of treatment with Tafamidis 61 mg):

- NIS (Neuropathy Impairment Score)
- NIS-LL (Neuropathy Impairment Score Lower Limbs)
- FAP (Familial Amyloidotic Polyneuropathy stage)
- PND (Polyneuropathy Disability Score)

5. *Have been diagnosed with ATTR amyloidosis polyneuropathy (ATTR-PN), based on any of the following criteria:*

- a. **Decreased amplitude in EMG studies, at least two nerves below normal, excluding median, or other nerve entrapment sites.**
- b. **A reduction in amplitude by more than 50% by at least two nerves above the patient's baseline value, excluding the median.**
- c. **Two different altered fine fiber tests (Sudoscan, CRS, RR interval variability, skin biopsy, etc.).**
- d. **A clinical picture consistent with small fiber neuropathy (painful or dysautonomic) and an altered fine fiber test.**

This inclusion criterion cannot be confirmed with the data collected in the CRF, so only the information collected in the yes/no variable of the screening criteria is considered.

A check will be carried out to ensure that the genotype (Mutation / Wild type) has been indicated for all patients.

Exclusion criteria

Patients who meet any of the following criteria will not be included in the study:

1. ***Treatment with Tafamidis free acid 61 mg for less than 12 months.***

In this section, refer to the inclusion criterion 3 check.

2. ***Not having a minimum of 12 months of neurological follow-up after starting treatment with Tafamidis free acid 61 mg.***

In this section, refer to the inclusion criterion 4 check.

3. ***Etiological diagnosis of polyneuropathy other than ATTR.***

No check with CRF.

Analyses will be performed with evaluable patients on the total population and subgroup based on genotype (ATTRv and ATTRwt).

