Tafamidis is a benzoxazole derivative without nonsteroidal anti-inflammatory activity that binds to TTR thyroxine binding sites with high affinity and selectivity. This leads to inhibition of dissociation of TTR tetramer into monomers, preventing the formation of amyloid fibers ([Bulawa CE, et al](#))¹⁴. Tafamidis 20 mg has been shown to slow the progression of peripheral neurological deterioration in patients with ATTR polyneuropathies (ATTR-PN) at stage 1 ([Coelho T, et al](#))¹⁵ and has been approved in Spain since 2011 for the treatment of transthyretin amyloidosis in adult patients with stage 1 polyneuropathy to delay peripheral neurological impairment (Information available on [AEMPS](#))¹⁶.

In the clinical trial to evaluate the safety and efficacy of tafamidis in transthyretin cardiac amyloidosis (ATTR-ACT), tafamidis at a dose of 20 mg and 80 mg (4 x 20 mg) was shown (compared to placebo) to reduce the combination of all-cause mortality and the frequency of cardiovascular-related (CV) hospitalizations, as well as to slow down the decline in functional capacity and quality of life (QoL) of patients with ATTR-CM of hereditary origin or wt ([Maurer MS, et al](#))¹⁷. Based on these outcomes, tafamidis obtained FDA and EMA approval for the treatment of patients with ATTR-CM (Information available at: [AEMPS; FDA](#))^{18,19}.

Upon completion of the ATTR-ACT study, patients had the option to participate in the extension study, LTE ([NCT02791230](#))²⁰ (B3461045), in which patients could be treated with tafamidis for an additional 60 months ([Damy T, et al](#))²¹. In the LTE, patients who in the ATTR-ACT study received tafamidis continued to receive the same dose, while patients who received placebo were randomly reassigned to receive tafamidis 80 mg or 20 mg at a 2:1 ratio. Following the July 20, 2018 protocol addendum, all patients were switched to 61 mg of tafamidis free acid, a new single capsule formulation that is bioequivalent to 80 mg of tafamidis meglumine used in the ATTR-ACT ([Lockwook PA, et al](#))²². Published outcomes show that tafamidis 80 mg/61 mg has greater efficacy by reducing all-cause mortality by 30% versus tafamidis 20 mg ([Damy T, et al](#))²⁰.

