9.2.1. Inclusion criteria

Patients must meet all of the following inclusion criteria to be eligible for inclusion in the study:

[figure not shown]
1. Be of legal age (>18 years).
2. Have participated in studies B3461028 and/or B3461045 in Spain.
3. Have been treated for at least 12 months with tafamidis free acid 61 mg.
4. Have a minimum of 12 months of neurological follow-up after starting treatment with tafamidis free acid 61 mg and have data from previous neurological evaluation or at the time of starting treatment with tafamidis free acid 61 mg.
5. Have been diagnosed with ATTR amyloidosis polyneuropathy (ATTR-PN), based on any of the following criteria:
 - a. Decreased amplitude in EMG studies, at least two nerves below normal, excluding median, or other nerve entrapment sites.
 - b. A reduction in amplitude by more than 50% by at least two nerves above the patient's baseline value, excluding the median.
 - c. Two different altered fine fiber tests (Sudoscan, CRS, RR interval variability, skin biopsy...).
 - d. A clinic compatible with small fiber neuropathy (painful or dysautonomic) and an altered fine fiber test.

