9.2.2. Exclusion criteria

Patients meeting any of the following criteria will not be included in the study:

1. Treatment with tafamidis free acid 61 mg for less than 12 months.
2. Not having a minimum of 12 months of neurological follow-up after starting treatment with tafamidis free acid 61 mg.
3. Etiological diagnosis of polyneuropathy other than ATTR.

PFIZER CONFIDENTIAL

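### The SAP check on the 12-month 61 mg criterion also passes patients with 12 months of 80 mg alone, which the protocol criteria do not provide for and the SAP does not declare

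*SAP*

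**What the plan says.** Protocol 9.2.1, inclusion criterion 3, reads "Have been treated for at least 12 months with tafamidis free acid 61 mg". Protocol 9.2.2, exclusion criterion 1, is its mirror image: "Treatment with tafamidis free acid 61 mg for less than 12 months". SAP 4.1 and 4.2 repeat both without change, the latter as "Treatment with Tafamidis free acid 61 mg for less than 12 months". None of these four places mentions 80 mg.

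SAP section 5 defines evaluable patients as "those who meet all of the inclusion criteria and none of the exclusion criteria described in the protocol". It then says how criterion 3 will be verified from the CRF dates. The first route uses the 61 mg start and end dates and asks for a gap of 12 months or more between them. A second route is enough by itself: "or otherwise the Tafamidis 80 mg end date minus its start date is at least 12 months". For a patient still on 61 mg, the date of inclusion in this study stands in as the end date. For exclusion criterion 1 the same section says only "In this section, refer to the inclusion criterion 3 check".

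The check for criterion 4 (12 months of neurological follow-up) works differently. It counts from the first date of treatment with either 61 mg or 80 mg, and exclusion criterion 2 is referred back to it. SAP 8.1.1 reports the durations on 80 mg and on 61 mg as separate variables.

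On background, Protocol section 7 says that after the addendum of 20 July 2018 "all patients were switched to 61 mg of tafamidis free acid", and describes the new capsule as bioequivalent to the 80 mg used in ATTR-ACT.

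**The concern.** The criteria and the check that is meant to enforce them are different rules. Patients can be classed one way by the criteria and another way by the check, and the SAP does not say which prevails. The primary objective is the effect of free acid 61 mg in ATTRv patients, yet the 80 mg branch can be met by someone with little or no 61 mg exposure.

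There is a second, separate difficulty inside the SAP. If 80 mg is meant to count towards the 12 months, one would expect time on the two formulations to be combined for a patient who moved from one to the other. The follow-up check runs across the switch. The exposure check tests each formulation alone.

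What is at stake is who enters a very small primary analysis set, and so the Month 12 NIS summary and the responder percentage in SAP 12.1.

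**Working it through.** No power or sample size figure bears on this point, so there is no plan figure to reproduce. The check compares the rules directly.

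**Inputs.** The criterion comes from Protocol 9.2.1 and 9.2.2 and SAP 4.1 and 4.2; the check from SAP 5; the expected numbers from SAP 4 (10 ATTRv and 10 ATTRwt). The documents give no patient-level durations, so the durations below are assumed for illustration.

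**Rules.** Let *a* be months on 80 mg and *b* months on 61 mg.

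- Criteria as written: *b* ≥ 12.
- SAP 5 check: *b* ≥ 12 or *a* ≥ 12.
- Combined exposure (stated in neither document; shown because it is the natural rule if both formulations count): *a* + *b* ≥ 12.

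| 80 mg (months) | 61 mg (months) | Criteria as written | SAP 5 check | Combined |
|---|---|---|---|---|
| 30 | 0 | fail | pass | pass |
| 30 | 6 | fail | pass | pass |
| 10 | 10 | fail | fail | pass |
| 11 | 11 | fail | fail | pass |
| 4 | 14 | pass | pass | pass |
| 30 | 40 | pass | pass | pass |
| 5 | 5 | fail | fail | fail |

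**Against the criteria as written**, the check errs in one direction only. It passes patients with *a* ≥ 12 and *b* < 12, who meet exclusion criterion 1. It never fails a patient with *b* ≥ 12, because that satisfies its first branch.

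**Against combined exposure**, it errs only the other way. It fails patients with *a* < 12, *b* < 12 and *a* + *b* ≥ 12. For 10 + 10 = 20 months, each branch sees 10 < 12. It never passes anyone whose combined exposure is under 12 months.

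**Follow-up.** Take the 10 + 10 patient, treated without a break and followed to the end of treatment. The criterion 4 check counts from the start of 80 mg and gives 20 months, a pass. The criterion 3 check gives 10 and 10, a fail. Criterion 4 itself, like criterion 3, names only the start of 61 mg.

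**Who can be affected.** From 20 July 2018 to the protocol date of 17 February 2022 is 1,308 days, and 1,308 / 30.4375 = 43.0 months. A patient switched soon after the addendum and still on 61 mg at inclusion has far more than 12 months of 61 mg and passes every rule. Those at risk stopped 61 mg within 12 months, switched late, or took only 80 mg.

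**Size per patient.** In the ATTRv set, 1/10 = 10%; in the total population, 1/20 = 5%. Two reclassified ATTRv patients would be 2/10 = 20%.

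**The case against.** The best defence is that the 80 mg branch is a deliberate and reasonable harmonisation. Protocol section 7 calls the two forms bioequivalent, Protocol 9.3 groups 80 mg and 61 mg as one treatment regimen, and Protocol 9.7 allows the SAP to modify the protocol's plans. That supplies a motive and a permission, but not a declaration. The SAP restates the 61 mg criteria unchanged, ties evaluability to the protocol, and its change log lists only sections 12.1 and 12.2.1.

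The CRF also records each criterion as Yes/No, so an investigator may already have flagged a patient under exclusion criterion 1. This stands as a partial safeguard. The SAP does not say whether the recorded answer or the date check decides when they disagree.

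Planned outputs would show part of the problem. SAP 5.1 shows non-evaluable patients with reasons, and SAP 8.1.1 gives the minimum duration on each formulation, so a 61 mg minimum below 12 months would be visible. That reveals a discrepancy after the fact but does not settle who belongs in the set.

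Two stronger readings are tempting. A reader might infer that failing to add the two periods also contradicts the protocol. It does not: a 10 + 10 patient has only 10 months of 61 mg and is excluded by the protocol's own wording, so this part conflicts only with the SAP's acceptance of 80 mg and its follow-up clock. A reader might also infer, because extension patients were switched, that misclassification is common. The documents do not support that either: being switched is not enough, and the 43-month interval leaves ample time for 12 months of 61 mg.

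**Conclusion.** The conflict is real and lies in the text. The SAP 5 check accepts 12 months of 80 mg alone, while the criteria it is meant to verify count only 61 mg. Reusing the check for exclusion criterion 1 lets a patient who meets a listed exclusion be classed as evaluable. The departure is not declared. The failure to combine periods is a separate inconsistency within the SAP.

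The number affected is not given and may be zero or small. The 10% figure is a per-patient weight that rests on the SAP's expectation of 10 ATTRv patients; it is not an estimate of how many are misclassified. Nor do the documents settle which exposure ought to qualify, and this point takes no position on that. It should be resolved before the analysis set is fixed, because in a set this small a single patient can visibly move the Month 12 result.

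**What to change.** Reconcile Protocol 9.2.1 and 9.2.2 with SAP 4.1, 4.2 and 5 to one stated qualifying-exposure rule, chosen by the sponsor. Apply it to inclusion criteria 3 and 4 and exclusion criteria 1 and 2.

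- If both formulations count, sum the time on each. Do not use first start to last stop, which would count any gap off treatment as exposure.
- If only 61 mg counts, remove the 80 mg branch and align the start date in the follow-up check.
- Where the rule departs from the protocol wording, declare it as a change with its reason.
- State whether the CRF Yes/No answer or the date check decides when they disagree.
- List every patient whose evaluability differs between the readings, and show the Month 12 NIS change and responder percentage in ATTRv both ways. If no patient differs, one sentence saying so is enough.

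The cost is revised wording, one derived exposure variable and a short sensitivity table. The start and end dates it needs are already used in SAP 5 and 8.1.1.
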